3.2.2. Secondary

See Section 11.4.4.2 for a discussion of the analysis populations utilized for the secondary outcome measures.

Secondary Outcome 1:

- The proportion of subjects who achieve a clinical response at Day 22 in each treatment group, including in all randomized subjects who took at least one dose of study medication.
 - “Clinical response” is defined as at least a 50% reduction in composite FLEET CAP score from baseline.

Secondary Outcome 2:

- The proportion of subjects who achieve a clinical response at Day 43 in each treatment group, including in all randomized subjects who took at least one dose of study medication.
 - “Clinical response” is defined as at least a 50% reduction in composite FLEET CAP score from baseline. Note that a subject who responds earlier before Day 43 does not need to achieve a clinical response at Day 43, as well.

Secondary Outcome 3:

- The mean, median, and quartiles of the FLEET CAP score at Days 22, 29 and 43 in each treatment group.
- The mean, median, and quartiles for each component of the FLEET CAP score at Days 22, 29 and 43 in each treatment group.
 - Cough
 - Fatigue
 - Chest Pain
 - Dyspnea (Shortness of breath)
 - Sputum production
 - Night Sweats
 - Fever
 - Hypoxia

Secondary Outcome 4:

-
- Number of days of school or work missed due to illness after the start of the treatment through Day 43 in each treatment group.
 - The mean, median, and quartiles for the mental component summary (MCS) and physical component summary (PCS) scores of the SF-12v2 instrument and the responses to the individual items of the PROMIS Item Bank v2.0 - Ability to Participate in Social Roles and Activities - Short Form 4a at Days 22, 29, 43, 90 and 180 in each treatment group.

Secondary Outcome 5:

- Incidence rate of all-cause mortality after the start of treatment and through Day 43 by treatment group.
 - Mortality information will be obtained through medical records or next of kin.

Secondary Outcome 6:

- The proportion of subjects who achieve a clinical response at Day 22 among all randomized subjects, regardless of coccidioidomycosis status or adherence to study drug, in each treatment group.

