should not be randomized. Subjects whose baseline ECG shows prolonged QTc interval may be asked to return for repeat 12-lead ECG prior to determination of eligibility status. Counseling regarding POC HIV testing and risk of false positives should occur by the site research team prior to the test being done.

- Enroll subjects in AdvantageEDC.
- Dispense the next available treatment assignment in sequence of study product (fluconazole or placebo) available at the site. Regardless of time the product is dispensed, observe subject taking 2 capsules (at once) in the clinic, and instruct subject to select a time of day to take their daily dose. If dosing cannot occur within 72 hours of the discharge from the facility where antibacterials for CAP were prescribed, then the subject should not be dosed and study activity must cease. Ideally, pills should be taken at the same time each day. Instruct subjects to bring their pill bottles to each visit. Review with subject that the study product should be stored at room temperature. Dispense 2 study product bottles (bottle A and B).
- Instruct subjects to notify the study center if they develop any severe reactions after study product dosing. If the site principal investigator or appropriate sub-investigator deems the reaction severe enough, further instructions will be given to the subject on the proper course of action, including a return to the clinic for immediate evaluation if appropriate.

Documentation of the subject's fulfillment of the entry criteria, for all subjects considered for the study and subsequently included or excluded, is to be completed. Documentation of screening failure details may be recorded using eligibility screening forms or a subject screen failure log. Screen failures will be entered in AdvantageEDC.

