7.3. Follow-up (Days 22-180, Visits 02-07)

7.3.1. Follow-up Visit Visit 02 (Day 22):

(Window: Day 20 to Day 23):

- Interview subjects and review the medical record for interim medical history, including an assessment for new medical conditions and symptoms, hospitalizations, diagnosis of disseminated coccidioidomycosis. Note any changes since the previous clinic visit.
- Perform a urine or serum pregnancy test on all women of childbearing potential. The test must be negative to ensure continued eligibility.
- Review any concomitant medications since previous study visit. Record all concomitant medications on the appropriate data collection form.
- Review of inclusion/exclusion criteria by clinician licensed to make medical diagnoses to determine continued eligibility.

-
- Perform a targeted physical examination if indicated based on review of complete medical history and any updates obtained by interview of subjects since the Day 1 visit by a clinician licensed to make medical diagnoses.
 - Record vital sign measurements (sitting blood pressure, sitting heart rate, respiratory rate, oral temperature, oxygen saturation and weight).
 - Query subject regarding whether the subject has taken their dose for today. If the subject has not yet taken their dose for today, subject should be instructed to take the day's dose in the clinic, prior to the pill count.
 - Perform a pill count of study product (fluconazole or placebo) and interview to determine adherence. Review need to bring pill bottles for count to each visit, study product dosing and storage requirements and ability to meet requirements with subject.
 - Following pill count, collect the pill bottle A and retain until study product accountability has been completed by the study monitor.
 - Note any discrepancies between expected and actual pill count remaining in pill bottle B.
 - Review randomization number assigned at Visit 01 and dispense final bottle (bottle C) of study product. Instruct the subject to continue to take daily doses from pill bottle B and to begin taking their daily doses from the newly dispensed bottle (bottle C) once bottle B is empty.
 - If subject did not return the pill bottle A dispensed at Visit 01, instruct them to return this bottle at their next visit.
 - Complete FLEET CAP Score
 - Collect the number of days missed from school and/or work due to illness for subjects who were either enrolled in school or employed at baseline

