11.4. Final Analysis Plan

11.4.1. Analysis Populations

Safety Analyses:

- Safety population – This safety analysis population includes all subjects who took at least one dose of study medication.

Efficacy Analyses:

- Intent-to-Treat (ITT) population – This efficacy analysis population includes all randomized subjects.
- Cocci Positive Modified Intent-to-Treat (mITT) population – This efficacy analysis population includes all randomized subjects who meet the case definition of coccidioidomycosis pneumonia and took at least one dose of study medication. Note that it is not necessary for a subject to be adherent to study drug to be eligible for inclusion in the mITT population.
- All Randomized Modified Intent-to-Treat (mITT) population – This efficacy analysis population includes all randomized subjects who took at least one dose of study medication regardless of cocci-status. Note that it is not necessary for a subject to be adherent to study drug to be eligible for inclusion in the mITT population.

- Cocci Positive Per-Protocol (PP) population – This efficacy analysis population includes randomized subjects who meet the case definition of coccidioidomycosis pneumonia who were compliant with the intervention administration and have coccidioidal serology data available at the Day 1 and 22 visits.
- All Randomized Per-Protocol (PP) population – This efficacy analysis population includes randomized subjects who were compliant with the intervention administration regardless of cocci-status and have coccidioidal serology data available at the Day 1 and 22 visits.

Adherence is assessed at each study visit depending on the fraction of expected pills taken on or before that time point. If at any visit the subject's cumulative fraction of pills taken drops below 80%, they are deemed non-adherent. This decision is not reversible, even if the subject's cumulative fraction of pills taken rises above 80% at a future visit.

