
(SO 4): To assess the impact of early empiric antifungal therapy with fluconazole on days lost from work or school and responses to the SF-12v2 and PROMIS Item Bank v2.0 - Ability to Participate in Social Roles and Activities - Short Form 4a in subjects with coccidioidomycosis pneumonia.
	
Number of days of school or work missed after the start of the treatment through Day 43 in each treatment group.
 
The mean, median, and quartiles for the mental component summary (MCS) and physical component summary (PCS) scores of the SF-12v2 instrument and the responses to the individual items of the PROMIS Item Bank v2.0 - Ability to Participate in Social Roles and Activities - Short Form 4a at Days 22, 43, 90 and 180 in each treatment group.
	
Descriptive and/or graphical summaries of the outcome measures by treatment group. This analysis will be performed in both PP populations, both mITT populations, and the ITT population.

(SO 5): To assess the effect of early empiric antifungal therapy with fluconazole through Day 43 in subjects with coccidioidomycosis pneumonia on all-cause mortality by treatment group.
	
Incidence rate of all-cause mortality after the start of treatment and through Day 43 by treatment group.
	
Descriptive summaries of the outcome measure by treatment group. This will be performed in both PP populations, both mITT populations, and the ITT analysis population.

(SO 6): To assess whether early empiric antifungal therapy with fluconazole at Day 22 is non-inferior to placebo as defined by clinical response at Day 22 in all randomized subjects, regardless of coccidioidomycosis pneumonia status or adherence with study intervention, with baseline and follow-up FLEET-CAP scores.
	
Proportion of clinical response at Day 22 among all randomized subjects, regardless of coccidioidomycosis status or adherence with study drug, in each treatment group.
	
Two-sided level .05 test of non-inferiority based on whether the 95% confidence interval for the difference in estimates of 22-day response proportions excludes an absolute difference of .05 in favor of the placebo arm. This analysis will be performed in the ITT population.

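### The two per-protocol mortality summaries for SO 5 start at first dose but admit only subjects who reached the Day 22 blood draw, so they understate mortality for the interval on their label

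*Combined protocol and SAP*

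**What the plan says.** Section 3.2.2 (Secondary Outcome 5) and the SO 5 row of Table 11 in Section 11.4.4.2 define the outcome as "Incidence rate of all-cause mortality after the start of treatment and through Day 43 by treatment group". The row calls for descriptive summaries by arm and then lists the sets: "This will be performed in both PP populations, both mITT populations, and the ITT analysis population".

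Section 11.4.1 defines the Cocci Positive PP population as cases "who were compliant with the intervention administration and have coccidioidal serology data available at the Day 1 and 22 visits". It defines the All Randomized PP population as randomized subjects "compliant with the intervention administration regardless of cocci-status and have coccidioidal serology data available at the Day 1 and 22 visits". The ITT and All Randomized mITT populations carry no serology condition.

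Treatment starts on Day 1, when staff must "observe subject taking 2 capsules (at once) in the clinic" (Section 7.2). The Day 22 visit has the range "Window: Day 20 to Day 23" (Section 7.3.1). On the source of the deaths, Section 3.2.2 states: "Mortality information will be obtained through medical records or next of kin". Sections 11.4.4 and 11.4.4.2 leave the details to a separate statistical analysis plan, which is not among the documents.

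**The concern.** Membership of either PP population depends on being alive about halfway through the interval over which mortality is to be reported. A death on Day 10 would be known to the trial from records or family, and would then be left out of both PP summaries because no Day 22 sample exists. The label on those summaries would still say that they cover start of treatment through Day 43.

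This deserves attention although SO 5 is only descriptive. Section 9.2.2 treats death as an efficacy endpoint and does not collect it as an SAE unless it is unexpected and suspected to be caused by study drug. SO 5 is therefore the main planned account, by arm, of most deaths. Two of its five summaries would give too low a figure, and a reader could take them as estimates for the whole 42 days.

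**Working it through.** The documents give no mortality rate, death count or power for SO 5, so there is no figure of theirs to reproduce.

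**Inputs from the documents**
- Start of the interval: Day 1 (Section 7.2). End: Day 43 (Section 3.2.2). Length: 43 − 1 = 42 days.
- Day 22 draw: Day 20 to Day 23 (Section 7.3.1), that is, 19 to 22 days after Day 1.
- Day 22 serology is required in both PP sets (Section 11.4.1).

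**Does anything waive the condition?** Three provisions come close, but none does.
- The adherence rule in Section 11.4.1 keeps data from before a subject becomes non-compliant. It neither lifts the serology condition nor moves the time origin.
- The early termination visit (Section 7.4.1) includes serology, but a sample taken there well before Day 20 is not Day 22 visit data.
- No landmark or delayed entry is described.

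**Survival time built into the PP sets**

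Share = (draw day − 1) / (43 − 1)
- Draw on Day 20: 19/42 = 45%
- Draw on Day 22: 21/42 = 50%
- Draw on Day 23: 22/42 = 52%

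**Effect on the figure.** Let m be mortality through Day 43 and e the share of deaths before the draw. Both are assumptions.

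*Read as deaths per subject:* PP figure = m(1 − e) / (1 − m·e). With m = 1% and e = 0.5 this is 0.5/99.5 = 0.50%, against 1% in the whole cohort.

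*Read as deaths per person-time:* split the 42 days into two halves of 21 days, with deaths uniform within each half. Write d1 = m·e and d2 = m(1 − e).
- Second-half person-days per cohort member: T2 = 21(1 − m) + 10.5·d2.
- Whole-cohort rate = m / [21(1 − d1) + 10.5·d1 + T2].
- PP rate from first dose = [d2/(1 − d1)] / [21 + T2/(1 − d1)].
- PP rate from Day 22 = d2 / T2.

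For m = 1% and e = 0.5, T2 = 20.79 + 0.0525 = 20.8425.
- Whole cohort: 0.01/41.79 = 0.239 per 1000 person-days.
- PP from first dose: 0.005025/41.947 = 0.120 per 1000 person-days.
- PP from Day 22: 0.005/20.8425 = 0.240 per 1000 person-days.

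Rates per 1000 person-days at m = 1%:

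| Share of deaths before draw (assumed) | Whole cohort | PP from first dose | PP from Day 22 | PP from first dose / whole cohort |
|---|---|---|---|---|
| 50% | 0.239 | 0.120 | 0.240 | 0.50 |
| 70% | 0.240 | 0.072 | 0.144 | 0.30 |
| 90% | 0.240 | 0.024 | 0.048 | 0.10 |

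The ratio is close to 1 − e and is essentially the same at m = 0.5% and m = 2%. Both readings of the rate give the same shortfall, so the immortal time is not a second reduction on top of the missing deaths. Starting the clock at Day 22 gives the right rate for Day 22 to Day 43. It does not recover the early deaths, as the 70% and 90% rows show.

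**The case against.** The strongest reply is that little depends on these two summaries. SO 5 has no test, alpha, power or decision rule, and the same row of Table 11 asks for ITT and both mITT populations. That stands, and it limits the point to labelling and choice of population. It does not make the PP figures correct for the interval they claim.

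Several stronger readings are tempting, and the documents do not support them.

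- **That early harm or benefit would be hidden.** It would not. ITT and All Randomized mITT are free of the serology condition, deaths are found without a visit, and these summaries sit beside the PP ones.
- **That half the person-time is certainly immortal.** The term incidence rate is not defined. If it means deaths per subject, there is no person-time to be immortal. The loss of early deaths remains under either reading.
- **That the shortfall is a known 50% or 70%.** Both figures rest on assumed timing. In absolute terms the numbers may be small: at an assumed 0.5% to 2%, 200 subjects (the planned Cocci Positive PP size) correspond to 1 to 4 deaths, of which half is 0.5 to 2.
- **That the comparison between arms is biased.** If the same share of deaths is lost in each arm, the level falls but the ratio hardly moves. Distortion needs early deaths to differ by arm, and the documents give nothing to size that.
- **That every death before Day 22 is lost.** The condition is the subject's own draw. Someone sampled on Day 20 who dies on Day 21 still counts.
- **That the non-adherence rule adds to the defect by cutting follow-up for anyone who stops capsules after Day 22.** It acts only at visits, and only below 80% cumulatively. A subject who stops after 34 of 42 daily doses is at 34/42 = 81% and stays in. This is ordinary per-protocol handling.
- **That the all-randomized sets should become the main SO 5 analysis.** The objective concerns subjects with coccidioidomycosis pneumonia, and the plan's own power calculation for the ITT comparison (Section 11.2.1) assumes that 80% of those enrolled are cocci-negative.

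**Conclusion.** The point holds in a limited form. By the text of Sections 3.2.2, 11.4.1 and 11.4.4.2, no death before a subject's own Day 22 draw can appear in either PP mortality summary, although both are labelled from start of treatment through Day 43. This needs no assumption.

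The size does. The understatement is roughly the share of deaths that precede the draw: about 50% if deaths are even over the 42 days, and more if they cluster early. If the rate is per person-time, 19 to 22 of the 42 days cannot contain a death.

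The consequence is confined to two of five descriptive summaries in one secondary objective. The separate analysis plan may define the rate, but as Table 11 stands both PP sets are included with no change of time origin.

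**What to change.** In the SO 5 row of Table 11, and in the matching analysis plan text, do one of the following:

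1. Remove both PP populations from SO 5. This agrees with SO 1 and SO 2, which use only the mITT and ITT sets, and with SO 6, which uses only ITT.
2. Keep them, start their clock at each subject's Day 22 visit, and label them 'mortality from the Day 22 visit to Day 43 among subjects who reached that visit'.

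Under either option, keep the cocci-positive mITT as the set that matches the objective. Add a note that case status there can depend on serology through Day 29 (Section 3.2.1), although two positive tests on Day 1 are enough under the first criterion. Report ITT and All Randomized mITT beside it as the summaries free of any survival condition. State whether the incidence rate is per subject or per person-time.

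The cost is one table row and some wording, with two fewer or two relabelled descriptive tables. No visit, sample size or error rate changes.

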 - Collect approximately 10 mL of venous blood for Hepatic function panel (AST, ALT, Alkaline phosphatase and total bilirubin), BUN, Creatinine. (will not need to be repeated if completed as part of pre-screening assessment)
 - Collect approximately 15 mL of venous blood for Coccidioidal serologies (CF; qualitative IDCF and IDTP; EIA-IgM; EIA IgG; and quantitative IDCF)
 - In addition the subject will be allowed the option to consent for additional sample collection (urine specimen, blood specimen [20 mL], nasopharyngeal swab, and throat swab) to be banked and used in future studies
 - The investigator will inform the subject of the results of the POC HIV -1 antibody test and provide counseling as to the meaning of the results, whether positive or negative. If the POC HIV-1 antibody test is positive and the participant does not have a prior diagnosis of HIV infection, the subject will no longer be considered eligible for participation in the study and the study product should not be administered. Counseling regarding the preliminary result and the need for a confirmatory test should be done by the site research team. A positive confirmatory test for those patients with a positive POC HIV testing will require counseling about the results and a recommendation to follow-up for care. Newly diagnosed HIV infections will receive additional counseling concerning the significance and possible risks to other people. Individuals with newly diagnosed HIV infections will be referred to the subjects clinical care provider and any other appropriate local resource. All test results, positive or negative, will be kept confidential to the extent permissible under the law. All positive results will be reported to the state's Division of Public Health as required by law. All confirmatory testing will be done following the institution's policy or the standard of care.
 - The investigator must review all safety laboratory results (including: AST, ALT, Alkaline phosphatase and total bilirubin, BUN, and creatinine), ECG results for QT prolongation, pregnancy test results, POC HIV test and eligibility criteria before the subject is randomized. Subjects who do not qualify for the study based on the results of the screening procedures

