11.2. Sample Size Considerations

11.2.1. Sample Size for Per Protocol Analysis Population

The primary analysis will compare the proportion of subjects achieving clinical response at Day 22 among efficacy evaluable subjects, defined as subjects in the Cocci-Positive Per Protocol analysis population who meet the case definition of coccidioidomycosis pneumonia who were compliant with the intervention administration and have coccidioidal serology data available at the Day 1 and 22 visits. We further assume that the clinical response proportion at Day 22 will be 0.20 in the placebo arm, and 0.40 in the fluconazole arm. As described in section 11.2.3, enrollment will continue until 200 subjects are evaluable for efficacy, 100 in each treatment arm, which suffices for 88% power for the Z test with unpooled variance to compare proportion of clinical responses at Day 22 at the two-sided level of 0.05. This is the primary sample size calculation which forms the basis for target enrollment to the study and for subsequent sample size re-estimation procedures at scheduled interim analyses while the study is enrolling.

A secondary analysis in the Cocci Positive Modified Intent-to-Treat population will compare the proportion of responders at Day 22, treating subjects dropping out before the Day 22 visit as non-responders. Assuming that the probability of drop-out before Day 22 is 20% among cocci-positive subjects, we would expect that 250 cocci-positive subjects would be available for this secondary analysis as a result of reaching the target sample size of 200 cocci-positive subjects with Day 22 follow-up for the primary analysis. Since subjects who drop-out are considered non-responders, the probability of response in the control-arm subjects would be $0.8 * 0.2 = 0.16$, and in the treated subjects would be $0.8 * 0.4 = 0.32$. The Z-test with unpooled variance has power of 85% to detect this difference in response proportions with 125 cocci-positive subjects per arm.

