A secondary analysis in the Intent-to-Treat population will compare the proportion of responders at Day 22 between fluconazole and control arms in all randomized subjects, using a two-sided level .05 test of non-inferiority with a margin of an absolute difference of 0.05. Subjects who drop-out before Day 22 will be imputed as non-responders for cocci-positive subjects, and as responders for cocci-negative subjects. Assuming that an enrolled subject has a 20% chance of being cocci-positive, and that the probability of response is 20% among cocci-positive subjects receiving control, 40% for cocci-positive subjects receiving treatment, and 70% for cocci-negative subjects, then the probability that a control subject responds is given by $0.2*(0.8*0.2 + 0.2*0.0) + 0.8*(0.8*0.7 + 0.2*1.0) = 0.64$, and the probability that a treated subject responds is given by $0.2*(0.8*0.4 + 0.2*0.0) + 0.8*(0.8*0.7 + 0.2*1.0) = 0.672$. The non-inferiority test has power of 78% if 1,000 subjects are enrolled, and 86% if 1,250 subjects are enrolled.

The power calculations in this section were performed with PROC POWER in SAS 9.4 or in R.

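### The all-comers non-inferiority test (SO 6) is valid as planned, but standardising it over the pre-dose Day 1 serology would keep the margin and could add about 0 to 5 points to its 78% power

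*Combined protocol and SAP*

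**What the plan says.** Section 11.4.4.2, Table 11 (SO 6), sets the test in the ITT population "based on whether the 95% confidence interval for the difference in estimates of 22-day response proportions excludes an absolute difference of .05" in favor of placebo. It names no stratification factor or covariate. Section 11.2.1 describes the same comparison "using a two-sided level .05 test of non-inferiority with a margin of an absolute difference of 0.05" and states: "The non-inferiority test has power of 78% if 1,000 subjects are enrolled, and 86% if 1,250 subjects are enrolled".

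Section 11.2.1 builds the two overall rates from a mixture. The share of cases is set by "Assuming that an enrolled subject has a 20% chance of being cocci-positive", and the response rates before drop-out by "the probability of response is 20% among cocci-positive subjects receiving control, 40% for cocci-positive subjects receiving treatment, and 70% for cocci-negative subjects". Drop-outs are handled by status: "Subjects who drop-out before Day 22 will be imputed as non-responders for cocci-positive subjects, and as responders for cocci-negative subjects".

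Section 7.2 lists, for every subject at Visit 01 and ahead of dispensing: "Collect approximately 15 mL of venous blood for Coccidioidal serologies". Section 4 also places a serology draw at randomization. The case definition in section 3.2.1 uses sera from Day 1 through Day 29, so the Day 1 result alone identifies only some of the eventual cases.

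Sections 11.4.4 and 11.4.4.2 leave analysis details to a separate statistical analysis plan, which is not among the documents reviewed.

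**The concern.** On the plan's own inputs the ITT population is 20% subjects who respond at 0.16 or 0.32 after imputation and 80% who respond at 0.76. An unadjusted difference treats the spread between these groups as noise. A pre-dose measurement related to group membership can remove part of that noise without changing what is estimated.

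SO 6 is the plan's formal test of empiric treatment in all comers regardless of coccidioidal status, and its stated power at the target enrollment is just under 80%. Any gain from data already collected needs no further subjects, visits or assays.

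**Working it through.** **Inputs.** From section 11.2.1: 20% cocci-positive; response 0.20 (control) and 0.40 (fluconazole) in cocci-positive subjects and 0.70 in cocci-negative subjects; margin 0.05; two-sided 0.05. Drop-out of 20% is stated for cocci-positive subjects, and the section's formulas apply it to cocci-negative subjects too. From section 5.3.1: 1:1 allocation, so n = 500 per arm at 1,000 subjects and 625 at 1,250.

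**Rates after imputation.**
- Cocci-positive control: 0.8 × 0.20 = 0.16. Cocci-positive fluconazole: 0.8 × 0.40 = 0.32.
- Cocci-negative, both arms: 0.8 × 0.70 + 0.2 × 1 = 0.76.
- Overall: 0.2 × 0.16 + 0.8 × 0.76 = 0.640, and 0.2 × 0.32 + 0.8 × 0.76 = 0.672. Both match the plan.

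**Step 1: reproduce the stated power.** Power = Φ((0.672 − 0.640 + 0.05)/SE − 1.96), with SE² = V/n.
- V = 0.64 × 0.36 + 0.672 × 0.328 = 0.4508.
- n = 500: SE = 0.03003; 0.082/0.03003 = 2.731; power 78.0%.
- n = 625: SE = 0.02686; 0.082/0.02686 = 3.053; power 86.3%.

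These agree with the stated 78% and 86%, so the stated power belongs to the unadjusted difference.

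**Step 2: standardise over Day 1 serology.** Estimate the difference within each stratum and average with weights equal to pooled stratum size. The target is still the overall risk difference. With share q in the Day 1-positive stratum,

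V = Σ (stratum share) × [p_c(1 − p_c) + p_t(1 − p_t)] + ½ q(1 − q)(d₁ − d₀)²,

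where d₁ and d₀ are the stratum-specific differences. The last term allows for the effect differing between strata.

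**Assumptions.** The documents give no accuracy for Day 1 serology against final case status. Sensitivity of 10-70% and specificity of 90-100% are assumed. Within each true status, response is taken not to depend on the Day 1 result.

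**Example, sensitivity 50%, specificity 100%.**
- q = 0.2 × 0.5 = 0.10. Positive stratum: 0.16 and 0.32.
- Negative stratum: the share of cases is 0.10/0.90 = 0.111, giving 0.693 and 0.711.
- Within-stratum sum: 0.10 × (0.1344 + 0.2176) + 0.90 × (0.2126 + 0.2054) = 0.4114.
- Effect term: ½ × 0.09 × (0.160 − 0.0178)² = 0.0009.
- V = 0.4124; SE = √(0.4124/500) = 0.02872; 0.082/0.02872 = 2.855; power 81.5%.

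**Power at 1,000 subjects (unadjusted 78.0%).**

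| Day 1 sensitivity | Specificity 100% | 95% | 90% |
|---|---|---|---|
| 10% | 78.6% | 78.0% | 78.0% |
| 20% | 79.3% | 78.3% | 78.1% |
| 30% | 80.0% | 78.8% | 78.4% |
| 50% | 81.5% | 80.1% | 79.3% |
| 70% | 83.1% | 81.6% | 80.6% |

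At 10% sensitivity and 90% specificity the Day 1 result carries no information about case status and the gain is nil. If Day 1 serology identified every case without false positives, V = 0.3643 and power is 85.9%. That is a ceiling.

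**Simulation check** (40,000 trials per setting). At 50%/100%, power was 81.6% adjusted against 78.0% unadjusted. Over the six settings simulated, with specificity 95% or 100%, the one-sided error with the true difference at the margin was 2.4-2.7% adjusted and 2.4-2.6% unadjusted.

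**The case against.** The strongest reply is that nothing here is wrong. The unadjusted comparison is valid, its power is correctly computed, and estimation detail is expressly left to a separate plan that may already adjust. All of that stands, and the point is limited to efficiency accordingly. It does not remove the point, because the main strategy and the power are both written in unadjusted form, and an adjustment carries most weight when fixed before unblinding.

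The second reply is that the gain may be negligible. Section 2.2 calls current tests insufficient in sensitivity and specificity, subjects are dosed within 72 hours of presentation, and the case definition provides for subjects who are negative on Day 1. A loose rule for calling Day 1 positive would also bring in false positives. This stands too, and is why the range starts at 10% sensitivity and includes 90% specificity. No setting computed loses power.

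Two stronger readings are tempting. A reader might set the 85.9% ceiling beside the plan's 86% at 1,250 subjects and infer that stratifying is worth 250 subjects. The documents do not support this: it would need Day 1 serology to identify every case, and the case definition relies on sera through Day 29. A reader might also infer that the plan disregards coccidioidal status in SO 6. It does use final status to impute drop-outs; what the stated test lacks is use of the Day 1 result to reduce variance.

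Stratifying on final case status would look more powerful but uses on-treatment sera. Section 11.4.4.1 itself plans to check for differential diagnosis between arms.

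**Conclusion.** The point holds as an optional improvement. SO 6 as written is valid and its 78% is right. Standardising over Day 1 serology leaves the estimand and the 0.05 margin unchanged and moves power at 1,000 subjects from 78.0% to about 78-83%, a gain of about 0 to 5 points. With half of the cases positive on Day 1, power is 81.5%, 80.1% or 79.3% at specificity 100%, 95% or 90%.

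The size rests on the plan's response, drop-out and prevalence inputs and on an assumed Day 1 accuracy that the documents do not give. The direction rests only on the serum being taken before the first dose and being related to case status. Whether the separate statistical analysis plan already adjusts cannot be judged from these documents.

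**What to change.** In Table 11 (SO 6) and the separate statistical analysis plan:

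- Make the SO 6 estimate a risk difference standardised over Day 1 serology strata, with weights equal to pooled stratum size, and compare its 95% confidence interval with the same 0.05 margin.
- Define before unblinding which Day 1 results count as positive, and give missing Day 1 results their own category.
- State that the variance includes the term for effects differing between strata.
- Keep the unadjusted interval as a supporting analysis.
- State that final case status is not used as the stratifier.

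Section 11.2.1 can keep its 78% and 86% as the unadjusted figures; any adjusted power should be given as a range with its accuracy assumptions. The cost is wording and a small amount of programming. The one complication is the missing-result category. No further subjects, visits or assays are needed.
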